- 2) Overdose Risk Assessment: This assessment is used to determine the potential for future overdose based on prior overdose history, current drug use practices and social context for current drug use. This assessment is not standardized but is compiled from individual items of known risk factors for overdose.
- 3) World Health Organization Quality of Life (WHOQOL-BREF). This is a short assessment to measure general health and physical, social and emotional functioning.
- 4) World Health Organization Alcohol, Smoking and Substance Involvement Screening Test (WHO-ASSIST v.3). This is a multi-item tool to determine areas of substance use and misuse. This assessment battery screens for recent and lifetime use of a variety of substances, including illicit drugs, alcohol, pharmaceuticals and tobacco products.
- 5) Age of First Use: Subjects are asked to provide the ages they first used a variety of substances.
- 6) HIV Risk Assessment Battery: This assessment is used to determine the potential for contracting HIV, hepatitis and other blood-borne illnesses based on drug use and sexual use behaviors.
- 7) Overdose History: This assessment will collect information related to any prior overdose that the subject has experienced or witnessed.
- 8) EQ-5D-3L: This validated quality of life measure asks about problems in mobility, self-care, usual activities, pain and discomfort, anxiety and depression and overall health.

Locator information:

Subjects will be asked to provide a number of sources to ensure they can be contacted for 3, 6 and 12 month follow-up visits. However, because we anticipate a number of high risk subjects to be indigent, subjects may be enrolled if they provide at least one primary source of locator information.

Randomization

Subjects will be randomized to receive either standard of care or the study intervention. We will recruit equal numbers of subjects in the intervention and control arms of the study, meeting eligibility criteria as heroin user or primarily pharmaceutical opioid users.

Follow-up Visits

Follow-up visits will occur at 3, 6 and 12-month after enrollment. All interviews will be by phone. Most assessments given at the baseline interview will be repeated at each follow-up

point. In addition to the assessments subjects will be asked questions about whether they have naloxone and, if not, what happened to any naloxone that was given to them.

Secondary Data Sources

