Secondary data on health care and drug treatment utilization will be obtained from Washington State (separate IRB action pending) using the following sources:

- Treatment and Assessment Report Generation Tool (*TARGET*) for drug treatment admissions data
- The Comprehensive Hospital Abstract Reporting System (CHARS) for hospital admissions

Information on any ambulance transports will be obtained from the Seattle Fire Department's Medic 1 unit.

In the event of a subject death during the study we will request information on cause of death from the King County Medical Examiner's Office. If a subject cannot be located we will also check this source to see if they have died and if so to obtain data on the cause of death. If we are unable to locate a subject during the course of the study or at final follow-up we will utilize the King County Jail Inmate Look-up Service. At no time will subjects be contacted or study procedures attempted while the subject is incarcerated.

Intervention Description

Standard care for patients who have used opioids would vary according to individual clinical need and might include referral to drug treatment or detoxification services. Standard care would not include OOPEN and BBCC interventions as specified in this grant. After baseline data are obtained subjects assigned to the intervention undergo the following procedures:

A brief behavior change counseling (BBCC) session

- Conveys subjects' risk for overdose, based on the baseline measures
- Engages them in a reflective discussion of the pros and cons of their current patterns of use
- Has the patients identify behavior change(s) they are interested in making to improve their health
- Encourages them to share opioid overdose prevention and intervention information and materials with their family, friends, housemates, and/or drug using partners.

Education and training on opioid overdose prevention and intervention with naloxone (OOPEN)

- Subjects will view a training video on study laptops that reviews:
 - Information on risk factors for overdose and how to prevent and reduce the risk of overdose

- How to recognize an opioid overdose
- The importance of calling 911
- How to intervene in an overdose
 - Positioning a victim in rescue position
 - Brief overview of rescue breathing
 - Training on how and when to administer naloxone

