- Subjects will be given a study brochure that covers the information in the video and reviews the Washington State 911 Good Samaritan overdose law which provides immunity from prosecution for drug possession charges to overdose victims and bystanders who seek aid in an overdose event.
- Prescribing and dispensing overdose rescue kits including 2 doses of intra-nasal naloxone, a disposable rescue breathing mask, and disposable gloves.
- Subjects in the intervention group will be informed that they may have one replacement of the naloxone kit (2 doses) during the 12 month study period.

We expect the intervention to take 30-45 minutes on average based on our experience and that this is feasible and reasonable for subjects and interventionists.

Fidelity assessment for the BBCC will be done with the shortened Motivational Interviewing Treatment Integrity (MITI) instrument.

Schedule of and Sources Data Obtainment

MEASURES	DATA SOURCES AND TIMING					
	Interview			Administrative		
	Case Report Form	Base-line	3 & 6 mos.	12 mo.	Up to 10 yrs.	Up to 10 yrs.
PRIMARY AIMS						
Aim 1: Overdose						
Subject overdosed prior 3/6* months	X		X			
Subject overdosed Y/N & Date						X
Aim 2: Drug use and other overdose risk behaviors						
Alcohol/Drugs 3/6 month use frequency	X		X		X	
Opioid use following interruption past 3/6 months	X		X		X	
Using opioids without others present	X		X		X	
Avg. daily opioid dose- Prescribed Opioid Users	X		X		X	
Opioid substitution drug treatment prior 3/6	X		X		X	
Other drug treatment sought or used prior 3/6	X		X		X	
SECONDARY AIMS						
Aim 3: Health care utilization						

ED, Outpatient, Inpatient and Ambulance- # & Aim 4: Health care costs Hospital-based total direct health care costs			x	x
Aim 5: HIV Risk Behaviors	x	x	x	x
CO-VARIATES & POTENTIAL EFFECT MODIFIERS				
Demographics	x			
Employment, health insurance, income, housing	x	x	x	
Alcohol/Drugs ages of first use	x			
Medical status and satisfaction (WHO QOL BREF, EQ-5D- 3L)	x	x	x	
Behavior change plans and readiness	x			
Overdose lifetime history	x			
Possessed, "carried" naloxone, # of days past 3/6	x	x	x	
Overdose # witnessed events past 3/6 months	x	x	x	
Source of naloxone- Study, other	x	x	x	
Subject had naloxone administered to them, #, by Disposition of naloxone	x	x	x	x
Subject had negative/allergic reaction to naloxone	x	x	x	
FIDELITY ASSESSMENT OF BASELINE				
Overdose prevention & intervention training. Item Motivational Interviewing Treatment Integrity 3.1.1	x			

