*Past 3 months timeline for 3 and 6 month follow ups, past 6 months used at 12 month follow up.

Brief Behavioral Change Counseling (BBCC)

The BBCC will be conducted according to the demeanor and guidelines of Motivational Interviewing (MI), a style for counseling patients about sensitive behaviors and for giving them information to enhance their health and safety in a non-judgmental manner. MI has been widely implemented in brief intervention studies for drug use and other behavior change. MI is non-confrontational and respectful of subjects' autonomy to discuss or not discuss sensitive topics. The BBCC will consist of 4 elements:

- 1) The interventionist will show to the patient an approximately 8-minute video on overdose prevention, recognition and intervention, which subjects will view on a laptop while they are using headphones. The interventionist will debrief the video with subjects and answer questions.
- 2) Next, the interventionist will review with subjects their overdose risk. This task involves informing subjects of the “good news” about overdose risks they are NOT incurring in their current behaviors for the purpose of reinforcing and hopefully continuing more positive health behaviors (e.g., not inappropriately mixing other drugs or alcohol with

opiates). Next, the interventionist will respectfully and in a neutral tone review with subjects the behaviors that currently place them at risk for opiate overdose (e.g., using opiates when alone or after a long period of abstinence).

- 3) From the video and risk feedback, the interventionist will segue into an open discussion of any changes subjects are thinking of making to increase their safety from overdosing. If at any time during the interview, subjects indicate that they would prefer to quit opiates or to seek opiate detox or treatment, the interventionist will help with these referrals. The discussion will culminate in a summary of healthy changes, if any, that subjects intend to make. Subjects will take with them a handout that has been customized to summarize any changes subjects indicate that they want to make.

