Several articles have been published showing the effectiveness of nasally administered naloxone in overdose situations and the comparability of effect between intranasal administration with other routes of administration for naloxone. The intra-nasal route of delivery of naloxone with a mucosal atomization device has been used in 1,000's of reversals safely and effectively by both medical professionals and lay persons.

According to the naloxone package insert "When administered in usual doses and in the absence of opioids or agonistic effects of other opioid antagonists, it exhibits essentially no pharmacologic activity." Its use on an unconscious person who did not use opioids is very likely to be benign.

There is no known mechanism by which naloxone could potentially be converted into an opioid agonist that could be abused. Nothing has ever been published that suggests such a conversion of naloxone has been accomplished and discussions with professors in schools of medicine ([name]) and pharmacology ([name]) at the University of Washington indicated no evidence that naloxone has ever been modified in such a way as to facilitate its being abused. According to the naloxone package insert: "NARCAN is an essentially pure opioid antagonist, i.e., it does not possess the "agonistic" or morphine-like properties characteristic of other opioid antagonists."

Subjects will be educated about withdrawal reactions. The overdose intervention training and all education materials will clearly and strongly encourage calling 911 during any suspected overdoses. Emergency medical services are well equipped to handle any withdrawal reactions. Intra-nasal administration of naloxone generally results in more mild withdrawal symptoms than other routes of administration.

Regulatory Compliance and Safety

Regulatory binder

The regulatory files should contain all required documents, study-specific documents, and all important communications. Regulatory files will be checked for compliance prior to study initiation, throughout the study, as well as at study closure.

Study documentation includes all case report forms, data collection forms, workbooks, source documents, monitoring logs and appointment schedules, sponsor-investigator correspondence, and signed protocol and amendments, or Institutional Review Board correspondence and approved current and previous consent forms and signed participant consent forms.

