The study was powered to address aim 1, the impact of the intervention on non-fatal overdose. For the study of each opioid user type (heroin and pharmaceutical opioids) the number of subjects needed in each arm of the study (intervention and comparison) to achieve power of 0.80 to detect a decline in the overdose rate from 20% to 10% at a confidence level of 0.05, is 219 subjects. To increase power somewhat and account for potential loss to follow up, we plan to enroll more subjects, 250 in each arm of each study, for a total of 500 heroin using subjects and 500 pharmaceutical opioid, non-heroin using subjects. Other outcomes to be analyzed include drug use and services utilization. Data on brief interventions in ED's shows declines in drug use and ED utilization of at least 40%. Specifically in Washington State, the Screening and Brief Intervention Referral and Treatment (SBIRT) found a 45% reduction in average days of drug use among high risk heroin users who received a brief intervention in an ED (from 15.8 days to 8.7 days in the prior month) and 41% reduction among high risk pharmaceutical opioid users (12.8 to 7.5 days).

Assumptions behind the power estimate are based upon an annual rate of non-fatal heroin overdose estimated to be a median of 25% across studies and for fatal overdoses approximately 1%. For the purposes of this sample size estimate we are conservatively assuming a total annual overdose rate for heroin users of 20%. We believe that a reduction of the OD rate by 50% may be possible based on the potential for additive effects of the OOPEN and the BBCC interventions. Preliminary data on overdose rates for pharmaceutical opioid

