Aim 1 Test whether the intervention group has lower rates of opioid overdose and longer time to occurrence of overdose. Overdose will be ascertained at 12 months via self-report and across at least 24 months via administrative data. Because randomized controlled studies are designed to account for potential confounding factors by distributing confounders, measured and unmeasured, equally across comparison and intervention groups, the initial unadjusted analysis will be a logistic regression analysis comparing the probability of opioid overdose in the two study arms. To examine differences in the time to overdose and to account for time varying covariates, such as overdose risk factors, survival analyses will be conducted with the outcome time to overdose(s). A Cox proportional hazards model will be used to investigate the possible association between these factors and event time. We will use sandwich standard error estimates in all statistical tests. Multivariable logistic regression analyses will be conducted to examine the association between predictors and moderators and of the odds of overdose occurrence. Predictors will include treatment assignment and overdose risk factors such as concomitant drug use, interruption in tolerance and homelessness. Potential effect modification will be assessed by including interaction terms for the treatment assignment by severity of opioid and other substance use as measured by the ASSIST. For the pharmaceutical opioid only group, effect modification by opioid user type will be assessed; opioid user typologies will be based upon which inclusion criteria subjects met.

Aim 2 Test whether the intervention group has fewer overdose risk behaviors. These are measured as both binary and continuous data. Binary data will be examined with logistic

regression and continuous data analyzed with ordinary least-squares regression. Analyses will adjust for the overdose risk behavior level or frequency reported at baseline as a concomitant variable, the outcome is the overdose risk behavior at 12 months, and the primary predictor is the treatment group assignment. We will compute robust standard error estimates for each model and use them in all hypothesis tests and confidence intervals.

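### As specified, a missed 3- or 6-month call leaves months in which self-reported overdose is never asked about; a since-last-interview question would cheaply reduce that gap (low priority)

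*Combined protocol and SAP*

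**What the plan says.** In the combined protocol and SAP, the schedule of measures lists the Aim 1 interview item as "Subject overdosed prior 3/6* months". The asterisk leads to the footnote "Past 3 months timeline for 3 and 6 month follow ups, past 6 months used at 12 month follow up". The follow-up calls are at months 3, 6 and 12, by phone.

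The Aim 1 text under Planned analyses gives self-report a defined role: "Overdose will be ascertained at 12 months via self-report and across at least 24 months via administrative data". The first Aim 1 analysis is a logistic regression on overdose yes or no, and a Cox model follows. The Sample Size Calculation section powers the heroin comparison on one-year rates and the pharmaceutical opioid comparison on two years of administrative follow-up.

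On repeat assessments, Follow-up Visits says only: "Most assessments given at the baseline interview will be repeated at each follow-up". The schedule table, which is damaged in extraction, appears to mark lifetime overdose history once.

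On contact, Locator information allows that "subjects may be enrolled if they provide at least one primary source of locator information", although several sources are requested and inability to give adequate contact information is an exclusion criterion. Secondary Data Sources provides a tracing step that begins "If we are unable to locate a subject during the course of the study or at final follow-up", and bars contact during incarceration.

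Missing data and dropouts plans to relate missingness to baseline values and to study arm. Its sensitivity analysis carries forward drug use; it does not mention overdose.

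**The concern.** The three windows cover months 0–3, 3–6 and 6–12 without overlap. The 12-month question reaches back only to month 6, so it cannot recover a missed 3- or 6-month call. A late call has a similar effect if the window is counted back from the call date: a 3-month call made at month 4 would cover months 1–4 and leave month 0–1 unasked.

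The outcome affected is a primary one. Dated administrative records would still pick up fatal and medically attended overdoses in the gap. An overdose that reached no record would be lost, and an interval nobody was asked about cannot be recovered at the analysis stage. The plan also does not say how such an interval is scored in the yes/no model.

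**Working it through.** **Inputs from the documents.** Windows of 3, 3 and 6 months (schedule footnote); 20% versus 10%, alpha 0.05, power 0.80, 219 per arm, 250 per arm enrolled (Sample Size Calculation).

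**Assumptions (not in the documents).** Constant hazard over the year; each early call missed independently with probability m = 10%, 20% or 30%, equally in both arms; 12-month call completed; gaps scored as no event; a share a of gap overdoses found in records, with a = 0 or 0.5.

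**1. The plan's own figure.** The two-sided two-proportion formula without continuity correction is

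n = [1.96·√(2·0.15·0.85) + 0.842·√(0.2·0.8 + 0.1·0.9)]² / 0.10² ≈ 199.

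With the continuity correction it gives 219, the stated figure, which is not in dispute. At 250 per arm, power is 88.2% uncorrected and 85.5% corrected.

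**2. Months covered when the 12-month call is completed.**
- No early call missed: 12 of 12.
- One missed: 9 of 12.
- Both missed: 6 of 12.

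Under a since-last-interview question all three cases give 12 of 12.

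**3. Observed one-year risk.** With λ = −ln(1 − p) and uncovered share u, the captured risk is 1 − exp{−λ[(1 − u) + a·u]}. For a = 0:
- u = 0: 20.0% and 10.0%
- u = 0.25: 15.4% and 7.6%
- u = 0.5: 10.6% and 5.1%

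These are averaged with weights (1 − m)², 2m(1 − m) and m². For m = 0.2 in controls: 0.64·20.0 + 0.32·15.4 + 0.04·10.6 = 18.2%.

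**4. Results, early calls missed equally.**

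| m | Observed risks, a = 0 | Risk ratio | Power, a = 0 (corrected) | Power, a = 0.5 | Control cases lost of 50, a = 0 / 0.5 |
|---|---|---|---|---|---|
| 0 | 20.0% v 10.0% | 2.00 | 88.2% (85.5%) | 88.2% | 0 / 0 |
| 10% | 19.1% v 9.5% | 2.00 | 86.5% (83.5%) | 87.4% | 2.3 / 1.1 |
| 20% | 18.2% v 9.0% | 2.01 | 84.7% (81.4%) | 86.6% | 4.6 / 2.3 |
| 30% | 17.2% v 8.6% | 2.01 | 82.7% (79.0%) | 85.7% | 6.9 / 3.4 |

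**5. What the rewording recovers if the 12-month call can also be missed at rate m.** Full-year coverage is (1 − m)³ with fixed windows and 1 − m with the reworded item.

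| m | Full-year coverage, fixed v reworded | Power, a = 0 | Power, a = 0.5 |
|---|---|---|---|
| 10% | 73% v 90% | 84.6% v 86.3% | 86.5% v 87.3% |
| 20% | 51% v 80% | 80.1% v 83.9% | 84.7% v 86.3% |
| 30% | 34% v 70% | 74.5% v 80.7% | 82.7% v 85.1% |

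With half of gap events on record, the gain is roughly 1 to 2 points of power. If the same people miss every call, it is nil.

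**6. Unequal misses, for illustration only.** Take equal true risks of 20%, with early calls missed at 30% in one arm and 10% in the other. The observed risks are 17.2% and 19.1%, a false difference of 1.9 points (0.9 with half on record). The standard error is about 3.5 points. The false difference favours whichever arm misses more calls.

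**The case against.** The best case against the point is that its effect is small and the plan already softens it.

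- **Enrolment margin.** The increase from 219 to 250 per arm was made partly for this purpose: "To increase power somewhat and account for potential loss to follow up, we plan to enroll more subjects".
- **Missingness by arm.** The planned check would show a differential pattern of missed calls. It would not recover any event.
- **Contact.** The exclusion for inadequate contact information and the tracing step should limit missed calls.
- **Other routes to an event.** Adverse events are asked about at each assessment with no recall limit stated, and follow-up questions cover what happened to study naloxone. Neither is stated to feed the Aim 1 outcome.
- **The form is not visible.** Most baseline assessments are repeated, and Overdose History may be among them. The finding is therefore that no catch-up is specified, not that none exists.
- **Recall.** The fix exchanges short uniform windows for unequal ones in subjects who missed a call, with more recall error there.

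All of this stands, and it sets the priority low. It does not remove the gap in the rule as written.

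Two stronger readings are tempting. One is that the gap biases the treatment comparison. That needs missed calls, or the share of overdoses reaching a record, to differ by arm, and the documents do not show this. Nor is the direction known: take-home naloxone could keep some overdoses out of the records in the intervention arm, while the training pulls the other way: "The overdose intervention training and all education materials will clearly and strongly encourage calling 911 during any suspected overdoses". The other is that power collapses because only subjects with unbroken self-report can be analysed; at m = 20% that would leave 250 × 0.64 = 160 per arm and about 71% power. Nothing in the plan proposes that restriction, and intention to treat is named as the primary approach.

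**Conclusion.** The point holds as a cheap improvement of low priority. Followed as written, the schedule leaves months 0–3, 3–6 or both unasked for a subject who misses an early call and completes a later one. The consequence is limited to unrecorded overdoses in the 12-month self-report part of Aim 1. It matters mainly for heroin users, since the power figure for pharmaceutical opioid users rests on two years of administrative data.

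With equal misses the risk ratio is essentially unchanged. Power falls by 1.7, 3.5 or 5.5 points at assumed miss rates of 10%, 20% or 30% with no gap event on record, and by 0.8, 1.6 or 2.5 points with half on record. These sizes depend on the assumed miss rates and on scoring gaps as no event, neither of which the documents give. A reader might infer that one reworded question closes the gap; it does so only up to the last completed call.

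**What to change.** 1. At each follow-up, ask about overdoses, with approximate month, since the last completed interview or, if there is none, since enrolment. Record the window length. Keep the 3/6-month windows for the Aim 2 items. If the interview form already works this way, correct the schedule footnote instead.
2. In the planned Cox analysis, censor self-report follow-up at the end of continuous coverage.
3. Add to the logistic model one overdose-specific sensitivity analysis that varies the assumed event rate in uncovered months by arm.

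**Cost.** One reworded item, one recorded variable, a sentence in the Aim 1 analysis text and one sensitivity analysis. Subjects who complete every call on time keep the same windows. Those who missed a call face recall of up to 12 months, with more recall error. Time after the last completed call, including after a missed 12-month call, is not recovered; steps 2 and 3 are there to deal with it.
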